### **10.3.4 Subgroup Analyses**

Subgroup analysis for the primary and secondary endpoints will be summarized by selected race groups. Additional subgroup analyses will be discussed in the study statistical analysis plan.

### **10.3.5 Interim Analyses**

No interim analyses are planned for this study.

## **10.4 Protocol Deviations**

The incidence of major protocol deviations will be summarized for the evaluable population.

Major protocol deviations will be determined before database lock. Details can be found in the statistical analysis plan.

## **11 QUALITY ASSURANCE AND QUALITY CONTROL**

### **11.1 Audit and Inspection**

Study centers and study documentation may be subject to Quality Assurance audit during the course of the study by the sponsor or its nominated representative. In addition, inspections may be conducted by regulatory authorities at their discretion.

## **12 QUALITY ASSURANCE AND QUALITY CONTROL**

### **12.1 Audit and Inspection**

Study centers and study documentation may be subject to Quality Assurance audit during the course of the study by the sponsor or its nominated representative. In addition, inspections may be conducted by regulatory authorities at their discretion

### **12.2 Monitoring**

Data for each subject will be recorded on a CRF. Data collection must be completed for each subject who signs an ICF and is administered study treatment.

In accordance with current GCP and, the study monitor will carry out source document verification at regular intervals to ensure that the data collected in the CRF are accurate and reliable.

The investigator must permit the monitor, the independent ethics committee (IEC)/IRB, the sponsor's internal auditors, and representatives from regulatory authority's direct access to all study-related documents and pertinent hospital or medical records for confirmation of data contained within the CRFs

### **12.3 Data Management and Coding**

The sponsor or sponsor's agent will be responsible for activities associated with the data management of this study. This will include setting up a relevant database and data transfer mechanisms, along with appropriate validation of data and resolution of queries. Data generated within this clinical study will be handled according to the relevant standard operating procedures of the data management and biostatistics departments of sponsor or agent.

Study centers will enter data directly into an EDC system by completing the CRF via a secure internet connection. Data entered into the eCRF must be verifiable against source documents at the study center. Data to be recorded directly on the eCRF will be identified and the eCRF will be considered the source document. Any changes to the data entered into the EDC system will be recorded in the audit trail and will be FDA Code of Federal Regulations 21 Part 11 compliant.

Missing or inconsistent data will be queried in writing to the investigator for clarification. Subsequent modifications to the database will be documented.

## **13 RECORDS AND SUPPLIES**

### **13.1 Device Accountability**

Not applicable.

### **13.2 Financing and Insurance**

Financing and insurance of this study will be outlined in a separate agreement between the sponsor and investigator's site.

## **14 ETHICS**

### **14.1 Independent Ethics Committee or Institutional Review Board**

Before initiation of the study at each study center, the protocol, the ICF, other written material given to the subjects, and any other relevant study documentation will be submitted to the appropriate IEC/IRB. Written approval of the study and all relevant study information must be obtained before the study center can be initiated. Any necessary extensions or renewals of IEC/IRB approval must be obtained for changes to the study such as amendments to the protocol, the ICF, or other study documentation. The written approval of the IEC/IRB together with the approved ICF must be filed in the study files.

The investigator will report promptly to the IEC/IRB any new information that may adversely affect the safety of the subjects or the conduct of the study. The investigator will submit written summaries of the study status to the IEC/IRB as required. On completion of the study, the IEC/IRB will be notified that the study has ended.

### **14.2 Regulatory Authorities**

Relevant study documentation will be submitted to the regulatory authorities of the participating countries, according to local/national requirements, for review and approval before the beginning of the study. On completion of the study, the regulatory authorities will be notified that the study has ended.

### **14.3 Ethical Conduct of the Study**

The investigator(s) and all parties involved in this study should conduct the study in adherence to the ethical principles based on the Declaration of Helsinki, GCP, and the applicable national and local laws and regulatory requirements.

### **14.4 Informed Consent**

The process of obtaining informed consent must be in accordance with applicable regulatory requirement(s) and must adhere to GCP.

The investigator is responsible for ensuring that no subject undergoes any study-related examination or activity before that subject has given written informed consent to participate in the study.

The investigator or designated personnel will inform the subject of the objectives, methods, anticipated benefits, and potential risks and inconveniences of the study. The subject should be given every opportunity to ask for clarification of any points s/he does not understand and, if necessary, ask for more information. At the end of the interview, the subject will be given ample time to consider the study. Subjects will be required to sign and date the ICF. After signatures are obtained, the ICF will be kept and archived by the investigator in the investigator's study file. A signed and dated copy of the subject ICF will be provided to the subject or their authorized representative.

It should be emphasized that the subject may refuse to enter the study or to withdraw from the study at any time, without consequences for their further care or penalty or loss of benefits to which the subject is otherwise entitled. Subjects who refuse to give or who withdraw written informed consent should not be included or continue in the study.

If new information becomes available that may be relevant to the subject's willingness to continue participation in the study, a new ICF will be approved by the IEC(s)/IRB(s). The study subjects will be informed about this new information and re-consent will be obtained.

#### **14.5 Subject Confidentiality**

Monitors, auditors, and other authorized agents of the sponsor and/or its designee, the IEC(s)/IRB(s) approving this research, as well as that of any other applicable agency(ies), will be granted direct access to the study subjects' original medical records for verification of clinical study procedures and/or data, without violating the confidentiality of the subjects to the extent permitted by the law and regulations. In any presentations of the results of this study or in publications, the subjects' identity will remain confidential.

## **15 REPORTING AND PUBLICATION, INCLUDING ARCHIVING**

Essential documents are those documents that individually and collectively permit evaluation of the study and quality of the data produced. After completion of the study (end of study defined as the date of the last visit of the last subject), all documents and data relating to the study will be kept in an orderly manner by the investigator in a secure study file. This file will be available for inspection by the sponsor or its representatives. Essential documents should be retained for 2 years after the final marketing approval or for at least 2 years since the discontinuation of clinical development of the investigational product. It is the responsibility of the sponsor to inform the study center when these documents no longer need to be retained. The investigator must contact the sponsor before destroying any study-related documentation. In addition, all subject medical records and other source documentation will be kept for the maximum time permitted by the hospital, institution, or medical practice.

The sponsor must review and approve any results of the study or abstracts for professional meetings prepared by the investigator(s). Published data must not compromise the objectives of the study. Data from individual study centers in multicenter studies must not be published separately.

4.0 INTRODUCTION

This statistical analysis plan (SAP) provides a more technical and detailed elaboration of the statistical analyses of the effectiveness and safety data as outlined and/or specified in the most recent protocol amendment of Study CMO-MA-PLS-0602 (version dated 20 Nov 2019). Specifications of tables, figures, and data listings are contained in a separate document.

Study CMO-MA-PLS-0602 is a multi-country, multi-center, non-randomized, open-label, single-arm, medical device post-marketing study in healthy volunteers with age ≥ 22 and ≤ 65 . All participants will undergo CoolSculpting® treatments(s) in an outpatient clinical setting. A treatment is comprised of timed segments of tissue cooling followed by massage.

[figure not shown]
The length of this study will be up to 20 weeks, not including the ≤ 7 days screening visit. Signed informed consent from the participants will be obtained before any study-related procedures are performed. All participants will be assigned a participant number sequentially based on the order in which the study participant is enrolled into the study. Participants meeting the inclusion criteria will be assigned to receive up to 2 treatment sessions 8 weeks apart and final follow-up 12 weeks after the final treatment (measured at week 12 for participants who receive 1 treatment session, or week 20 for 2 treatment sessions). Participants withdrawing from the study will be encouraged to complete the same final evaluations as participants completing the study according to this protocol, particularly safety evaluations.

No interim analyses are planned for this study.

Allergan Confidential
CoolSculpting[®]

Statistical Analysis Plan CMO-MA-PLS-0602

5.1 **OBJECTIVES**

Primary Objective

The primary objective is to evaluate overall patient satisfaction for non-invasive fat reduction in CoolSculpting® participants.

Secondary Objectives

1. To evaluate overall satisfaction for non-invasive fat reduction in abdomen alone, flank alone, and abdomen and flanks in CoolSculpting® participants.
2. To evaluate overall satisfaction for non-invasive fat reduction in CoolSculpting® participants by number of treatment cycles.
3. To evaluate overall satisfaction for non-invasive fat reduction in CoolSculpting® participants by BMI (normal: 18.5 to <25, overweight: 25 to ≤30).
4. To evaluate change in volume of fat after CoolSculpting® treatment(s) using 3D photography.
5. To determine the frequency of AEs, including SAEs; and ADEs including SADEs.

[REDACTED]

1. [REDACTED]

[REDACTED]

[REDACTED]

[REDACTED]

6.1 PARTICIPANT POPULATIONS**6.2 ENROLLED POPULATION**

The enrolled population will consist of all participants who sign the informed consent form.

6.3 EVALUABLE POPULATION

The evaluable population will consist of all participants who sign the ICF, have at least one of the procedures conducted, and also report the CSQ Item #1 at 12 weeks after the final treatment (measured at Week 12 for participants who receive 1 treatment session and at Week 20 for participants who receive 2 treatment sessions).

6.4 SAFETY POPULATION

The safety population will consist of all participants who have at least one of the procedures conducted.

6.5 OTHER POPULATIONS

Not applicable.

6.6 DATA COLLECTED BUT NOT ANALYZED

Not applicable.

7.1 **PARTICIPANT DISPOSITION**

The number of participants who are in the enrolled population and the number and percentage of participants who are in the safety population and evaluable population will be summarized.

The number and percentage of participants who complete the study and who prematurely discontinue from study will be presented for enrolled population; furthermore, the number and percentage of participants discontinued prematurely from study will be presented by the primary reason for discontinuation as collected on the eCRF. Reasons for pre-mature discontinuation from the study include:

- Physician decision
- Protocol deviation
- Screen failure
- Site terminated by sponsor
- Study terminated by sponsor
- Technical problems
- Withdrawal by subject
- Lost to follow up
- Other

8.1 **DEMOGRAPHICS AND OTHER BASELINE DATA**

8.2 **DEMOGRAPHICS**

Demographic parameters will be summarized descriptively for the safety and evaluable populations. Demographic parameters include age, age group (22-29, 30-39, 40-49, 50-59, 60-65), sex, and race (White, Black, Asian – Chinese, Asian – Japanese, Asian – Korean, Asian - Other, Arab/Middle Eastern, Other, Choose not to answer). Age will be calculated in years from year of birth to the informed consent date.

8.3 **BASELINE CHARACTERISTICS**

Baseline characteristics will be summarized descriptively for the safety and evaluable populations. Baseline characteristics include weight, height, Fitzpatrick Skin Type (I, II, III, IV, V, VI), body mass index (BMI), and BMI category (18.5 - <25, 25 - ≤30); where BMI is calculated as weight [kg]/(height [m])².

8.4 **MEDICAL AND SURGICAL HISTORIES**

Abnormalities in participants' medical and surgical histories will be coded using the Medical Dictionary for Regulatory Activities (MedDRA), version 22.0 or newer. The number and percentage of participants with abnormalities in medical and surgical histories in each system organ class and preferred term will be summarized for the Safety Population.

The summary table by SOC and PT will be presented with SOC in alphabetical order and in decreasing frequency within each SOC. If more than one medical and surgical history term is coded to the same preferred term for the same participant, the participants will be counted only once for that preferred term.

8.5 **PRIOR AND CONCOMITANT MEDICATIONS**

Prior medication is defined as any medication taken before the date of the first study treatment. *Concomitant medication* is defined as any medication taken on or after the date of the first study treatment. World Health Organization (WHO) Drug Dictionary, Global B3 version 201903 or newer, will be used to classify prior and concomitant medications by therapeutic class and drug name.

The number and percentage of participants with use of prior medications will be summarized by WHO drug class and preferred drug name for the Safety Population. Similarly, the number and percentage of participants with use of concomitant medications will be summarized by WHO drug class and preferred drug name for the Safety Population. If a participant took a specific medication multiple times or took multiple medications within a specific therapeutic class, that participant would be counted only once for the coded drug name or therapeutic class. Formulations (including salts, esters, etc.) containing the same active ingredient will be pooled under the coded drug name of the base compound. Medications containing multiple active ingredients of different coded drug names will be reviewed during the course of the study and may be pooled under a single coded drug name for analyses.

8.6 PROTOCOL DEVIATIONS

The number and percentage of participants with important protocol deviations will be summarized for all participants. Deviations related to the following categories will be included:

- Inclusion or exclusion criteria
- Withdrawal criteria
- Treatment
- Concomitant medications

Protocol deviations will be reviewed and documented before database lock.

9.1 EXTENT OF EXPOSURE AND TREATMENT COMPLIANCE**9.2 EXTENT OF EXPOSURE**

For each treatment area, the treatment duration in each treatment cycle will be calculated as the number of minutes from the time of treatment cycle start to the treatment cycle end; the treatment duration in a treatment session is the sum of the treatment durations from all treated cycles. Descriptive statistics (n, mean, SD, minimum, median, and maximum) will be presented by treatment session cycle and by treatment area.

In addition, descriptive statistics will be presented for combined treatment sessions; and similarly, for combined upper and lower abdomens, combined right and left flanks, and for all treatment areas combined. The treatment duration for the combined treatment areas is defined as sum of the treatment durations from the corresponding treated areas, regardless of overlapped duration.

Number and percentage of participants with treatment interrupted or discontinued along with the reason will be presented by treatment session and by treatment area.

9.3 MEASUREMENT OF TREATMENT COMPLIANCE

The study investigators are responsible for performing the study in compliance with the protocol. The treatment compliance will not be applicable in the study.

10.1 EFFECTIVENESS ANALYSES

The effectiveness analyses will be based on the evaluable population. Baseline is defined as the last non-missing assessment before the first cycle of treatment.

In addition to the entire evaluable population, summaries will be provided for the following cohorts:

- Participants with 1 treatment session
- Participants with 2 treatment sessions

Some effectiveness parameters are also measured or reported at 8 weeks post treatment session #1. Descriptive summaries will be provided for this visit similar as for the effectiveness endpoints at the final visit.

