##### 9.1.1.1 Cryolipolysis Satisfaction Questionnaire (CSQ) Subject Satisfaction Patient-Reported Outcome Survey

The CSQ is a 4-item PRO instrument that measures patient satisfaction with CoolSculpting treatment of the flank and abdomen. The questionnaire assesses patient satisfaction with treatment, visible fat reduction, improvement in fit of clothing, and overall effect of treatment. The CSQ consists of 3 versions: CSQ-Abdomen ([Appendix 17.4](#)), CSQ-Flank ([Appendix 17.5](#)), and CSQ-Abdomen and Flank ([Appendix 17.3](#)). Initial draft of the questionnaire was developed based on questions used in previous CoolSculpting studies and was revised based on hybrid concept elicitation and cognitive debriefing interviews with 6 patients.

The CSQ will be administered during office visits before treatment at Week 8 (Visit 4a) and during follow-up/exit visits at Weeks 12 (Visit 6, for patients who receive 1 treatment session) and 20 (Visit 7, for patients who receive 2 treatment sessions). Patients with abdomen only treatment will only be administered the CSQ-Abdomen version. Patients with flank only treatment will only be administered the CSQ-Flank version. Patients with both abdomen and flank treatment will be administered all 3 CSQ versions: CSQ-Abdomen, CSQ-Flank, and CSQ-Abdomen and Flank.

[REDACTED]

[REDACTED]

[REDACTED]

[REDACTED]

[REDACTED]

[REDACTED]

[REDACTED]

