### **10.3.2 Efficacy Analyses**

The evaluable patient population will be the analysis population used for efficacy.

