The count and percentage of participants with the same categories as the primary endpoint for CSQ Item #1 will be summarized and the 95% CIs for the percentages will be calculated.

Descriptive summary statistics of change in volume of fat from baseline will be provided by visit.

[REDACTED]

[REDACTED]

[REDACTED]

[REDACTED]

[REDACTED]

[REDACTED]

[REDACTED]

[REDACTED]

[REDACTED]

- █ [REDACTED]
- █ [REDACTED]
- █ [REDACTED]
- █ [REDACTED]
- █ [REDACTED]

[REDACTED]

[REDACTED]

[REDACTED]

[REDACTED]

[REDACTED]

11.1 **SAFETY ANALYSES**

The safety analyses will be based on the safety population.

11.2 **ADVERSE EVENTS**

Adverse events (AEs) will be collected throughout the study beginning with the first treatment visit. Adverse events will be coded by system organ class and preferred term using the *Medical Dictionary for Regulatory Activities*, version 22.0 or newer. AEs, AE severity, and causality are defined in the protocol (Section 11.1).

An AE will be considered a treatment-emergent (TEAE) if the AE began or worsened (increased in severity or became serious) on or after the treatment start date and time. An AE is considered an ADE if the AE with a reasonable possibility (Possible, Probable, or Causal relationship) that the device caused the event. An AE is considered a study procedure related AE if the AE with a reasonable possibility (Possible, Probable, or Causal relationship) that the procedure caused the event.

Overall summary of TEAEs, SAEs, ADEs, SADEs, study procedure related AEs, TEAEs leading to study discontinuation, and deaths will be presented as total and by treatment session. AEs/ADEs occurred on or after the date of treatment sessions 1 and before the date of treatment session 2 are counted for treatment session 1; AEs/ADEs occurred on or after the date of treatment sessions 2 are counted for treatment sessions 2.

The number and percentage of participants will be summarized by System Organ Class (SOC) and Preferred Term (PT), with or without by severity, as total and by treatment session as follows:

- TEAEs by SOC and PT
- TEAEs by SOC, PT, and severity
- ADEs by SOC and PT
- ADEs by SOC, PT, and severity
- Study Procedure Related AE by SOC and PT
- Treatment-emergent Serious AEs (SAEs) by SOC and PT
- Serious ADEs (SADEs) by SOC and PT
- TEAEs leading to study discontinuation by SOC and PT

The AE summary tables by SOC and PT will be presented with SOC in alphabetical order and in decreasing frequency within each SOC.

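### Week 8 and fat-volume summaries leave out treated participants who have the measurement but no final CSQ Item #1 answer

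*SAP*

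**What the plan says.** Protocol 10.3.2 sets one population for all efficacy work: "The evaluable patient population will be the analysis population used for efficacy". SAP 10.1 repeats the rule without qualification: "The effectiveness analyses will be based on the evaluable population". Under SAP 6.3, a participant is evaluable only if they consented, had at least one procedure, and "also report the CSQ Item #1 at 12 weeks after the final treatment". That means Week 12 after one session or Week 20 after two.

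SAP 10.1 goes on: "Some effectiveness parameters are also measured or reported at 8 weeks post treatment session #1". It then adds: "Descriptive summaries will be provided for this visit similar as for the effectiveness endpoints at the final visit". Protocol 9.1.1.1 confirms that the CSQ is given at the Week 8 visit. For the 3D endpoint, SAP 10.3 says: "Descriptive summary statistics of change in volume of fat from baseline will be provided by visit". No readable text gives the Week 8 or volume summaries a different population.

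A population without the final-answer condition already exists in SAP 6.4: "The safety population will consist of all participants who have at least one of the procedures conducted". The SAP uses it for safety, exposure and baseline tables, but not for effectiveness.

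**The concern.** A Week 8 answer enters the Week 8 table only if the same person answers again 4 weeks later (one session) or 12 weeks later (two sessions). The Week 8 result is thus conditioned on a future event. Likewise, a volume change measured by 3D photography enters its table only if a separate questionnaire item was completed at the end of the study.

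This differs from the question of how to handle a missing primary answer, because here the measurement exists and the summary leaves it out. If people who do not give a final answer differ from the rest in Week 8 satisfaction or in volume change, the reported figures describe a selected group. The study is single-arm, so no comparator offsets such selection. Protocol 7.3.4 does not replace participants who leave.

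**Working it through.** **Inputs** (Protocol 10.1 and SAP 15.0): prior rates of 65.8% in 19 and 63.3% in 60; 98 participants for a 10% margin of error; 10% dropout; about 108 recruited.

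**Step 1: the plan's own figures.**
- Weighted rate: (19×65.8 + 60×63.3)/79 = 5048.2/79 = 63.9%. Reproduced.
- Recruitment: 98×1.1 = 107.8, so 108. Reproduced (98/0.9 gives 109).
- Margin at n = 98 by normal approximation: 1.96×√(0.639×0.361/98) = 9.5%, inside the target. That formula alone needs only 89. The exact interval has a half-width of 9.9% at 98. Nothing below depends on which method was used.

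**Step 2: how many could be left out.** 108×0.9 = 97.2, so about 97 are evaluable and 11 are not. Eleven is a ceiling for the Week 8 summary, since some of the 10% may leave before treatment or before Week 8.

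**Step 3: effect on the Week 8 rate.** Assumptions: the rate among the 97 evaluable participants is 63.9% (the plan's figure for the final visit, borrowed for Week 8), and *L* leavers answered at Week 8, of whom a share *s* were satisfied. The all-available rate is

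(97×0.639 + *L*×*s*)/(97 + *L*), with 97×0.639 = 61.98.

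| *L* | *s* | All-available rate | Plan reports | Plan minus all-available |
|---|---|---|---|---|
| 11 | 0% | 61.98/108 = 57.4% | 63.9% | +6.5 points |
| 11 | 20% | 64.18/108 = 59.4% | 63.9% | +4.5 |
| 11 | 40% | 66.38/108 = 61.5% | 63.9% | +2.4 |
| 11 | 63.9% | 63.9% | 63.9% | 0 |
| 11 | 100% | 72.98/108 = 67.6% | 63.9% | −3.7 |
| 5 | 0% | 61.98/102 = 60.8% | 63.9% | +3.1 |
| 5 | 40% | 63.98/102 = 62.7% | 63.9% | +1.2 |
| 5 | 100% | 66.98/102 = 65.7% | 63.9% | −1.8 |

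Protocol 7.3.1 gives approximately 100 enrolled rather than 108. With 90 evaluable and 10 leavers the extremes are 57.5% and 67.5%, or +6.4 and −3.6 points, so the choice hardly matters.

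**Step 4: precision.** The normal-approximation margin is 9.6% at n = 97 and 9.1% at n = 108. The loss of precision is small, so selection is the issue.

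**Step 5: fat volume.** The mean moves by the fraction left out times the difference between those left out and those kept. With 10% left out and an assumed difference of 0.5 SD, that is 0.10×0.5 = 0.05 SD. The documents give neither the number with an image but no CSQ answer nor the difference, so this is illustrative only.

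**The case against.** The case for leaving the plan alone has several parts.

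- **Low stakes.** Protocol section 10 says there is no hypothesis to prove. Week 8 satisfaction is neither the primary nor a listed secondary endpoint. This stands, and it limits the weight of the point.
- **A fixed set of people is a legitimate choice.** It lets Week 8 and final results be compared in the same participants. This also stands, but a supportive evaluable-only table preserves the comparison.
- **Week 8 imaging is not documented.** The schedule of assessments is not in the supplied text, SAP 10.1 speaks only of some parameters at Week 8, and the secondary endpoints are placed at Week 12 or 20. Week 8 volume is an inference from the by-visit wording. The final-visit volume point does not need that inference, but it affects only people imaged at that visit who leave the CSQ item unanswered, probably few.
- **Early leavers may still be captured.** Withdrawing participants are encouraged to complete the final evaluations, which reduces the loss without removing it. SAP 17.2 assigns to the final visit the last available assessment after treatment start. Read literally, a Week 8 answer could fill that slot. SAP 6.3 still requires the answer at 12 weeks after the final treatment, so this is an ambiguity to reconcile and does not answer the point.
- **Redacted text might name another population.** It might, but the SAP 10.1 rule is general and SAP 18.0 declares no change from the protocol.

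A reader might infer that dissatisfied people leave more often, so that the plan inflates Week 8 satisfaction. That is plausible, but the documents offer no evidence on why people leave, and satisfied participants may also skip a last visit. A reader might also infer that data are destroyed. SAP 17.1 generally provides listings, so the omission is from summary tables.

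**Conclusion.** The point holds in limited form and is a cheap improvement. As written, the plan leaves observed Week 8 CSQ answers and 3D volume measurements out of their summaries because of a later or unrelated non-response.

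Under the assumptions in the working (97 evaluable at 63.9%, all 11 leavers answering at Week 8), the reported Week 8 rate lies between 6.5 points too high and 3.7 points too low. With about 5 leavers after Week 8 it is at most 3.1 points too high. These are extremes, and the direction is not known. The volume effect cannot be sized from the documents, and any effect on Week 8 volume depends on imaging having been done then.

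It would be wrong to conclude that the main result is biased by this rule on Week 8 and volume data. The primary analysis uses the final CSQ Item #1 answer and is unaffected. The summaries concerned are descriptive.

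**What to change.** In SAP 10.1:

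1. Keep the evaluable population for the final-visit CSQ Item #1 analyses.
2. Summarise Week 8 measures in all treated participants (the safety population) who have that measurement.
3. Summarise 3D volume change in all treated participants with a baseline image and an image at the visit in question, whatever their CSQ response.
4. Show n for each endpoint and visit.
5. Optionally keep the evaluable-only version as a supportive table for comparison within the same participants.
6. Record the departure from Protocol 10.3.2 in SAP 18.0, which at present declares none.

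The cost is a few sentences of SAP text and some table programming, with no new data. The drawback is that denominators will differ between endpoints and visits, which is why n must be shown.
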